## 11.2 WP1 (main trial) Analysis

Data will be reported and presented according to the CONSORT extension for stepped wedge cluster randomised trials[36] and analysed in accordance with a detailed statistical analysis plan.

#### 11.2.1 Analysis populations

Modified Intention-to-treat population (mITT): composed of all consented participants with outcome data, regardless of protocol deviations or withdrawals. Participants will be analysed based on the intervention they were supposed to receive.

Intention-to-treat population (ITT): composed of all consented participants, regardless of protocol deviations, withdrawals, or the availability of outcome data. Participants will be analysed based on the intervention they were supposed to receive. Outcome data will be imputed under different assumptions for this analysis population.

Per-protocol population (PP): composed of all consented participants with outcome data, who received treatment as per the protocol, and had no major protocol deviations.

## 11.2.2 Statistical analysis

The number of days using NIV >4hrs at week 9-12 following NIV initiation will be analysed using a poison mixed effect model with intervention, step (time) and cluster level randomisation factors (centre size, telemonitoring use and location of initiation) as fixed effects and site as a random effect. Effect sizes will be summarised as the absolute difference in mean days along with its 95% confidence interval and p-value. The primary analysis will be on the ITT analysis population with secondary analysiss for the PP analysis populations.

Continuous secondary outcomes will be analysed in the same way as the primary outcome. A logistic regression will be undertaken to analyse binary secondary outcomes using a model similar to that for the continuous outcomes. Differences between treatment groups will be reported as odds ratios with associated 95% confidence intervals and p-values. Time to event data will be analysed using a shared frailty Cox model. Secondary outcomes will be analysed for the ITT population.

Methods for handling missing outcome data across the analyses will be described in the statistical analysis plan.

Additional exploratory analyses will investigate whether participant and disease characteristics (e.g. age, sex, time since symptom onset, presence of upper airway secretions) are potential predictors of NIV use or moderators of treatment efficacy.

WP2 (process evaluation) analysis please see section 12.2.

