## 8.1 Primary outcome/endpoint

NIV usage at 12 weeks (the number of days in which patients use NIV for >4hr/day during week 9-12).

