## 11. Statistics

#### 11.1 Sample size

The primary outcome is the number of days in which patients use NIV for >4hr, assuming standard deviation of ten0 days with a high skew. A modest change in survival and quality of life requires a large change in adherence; we assume a mean difference of six days to reflect this. Assuming a

conservative estimate where each site recruits, on average one patient per month in months 7-24 and three patients in the six months roll in period this will recruit a total of 252 patients. Allowing for 15% drop-out, 214 participants provide 90% power to detect an increase of six days in adherence assuming an inter-cluster coefficient of 0.05 and a two-sided 5% significance level. The sample size was calculated using a modified version of the Stata stepped wedge macro which allowed non-integer number recruited per step.

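### The Poisson mixed model named for the primary outcome fixes the within-site variance at the mean, against a planned SD of 10 days; with model-based standard errors the 5% test would reject a true null in roughly 28–50% of trials

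*Protocol*

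**What the plan says.** Protocol section 8.1 defines the primary outcome as "the number of days in which patients use NIV for >4hr/day during week 9-12". Four weeks make this a count from 0 to 28.

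Section 11.2.2 states that the outcome "following NIV initiation will be analysed using a poison mixed effect model with intervention, step (time") and the three cluster-level randomisation factors "as fixed effects and site as a random effect". It then says "Effect sizes will be summarised as the absolute difference in mean days along with its 95% confidence interval and p-value". The word printed as poison is plainly Poisson. The section names no dispersion parameter, patient-level random effect, scaled standard error or robust standard error.

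Section 11.1 sizes the trial "assuming standard deviation of ten0 days with a high skew". It adds "we assume a mean difference of six days to reflect this", and states that "214 participants provide 90% power to detect an increase of six days in adherence" with an "inter-cluster coefficient of 0.05 and a two-sided 5% significance level". The protocol gives no mean number of days for either arm.

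**The concern.** The two sections describe different variances for the same outcome. Conditional on site and covariates, a Poisson model has no free variance: it equals the mean. Since the mean cannot exceed 28, the within-site SD the model allows cannot exceed 5.3 days. The planning SD is about twice that.

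The site random effect takes up between-site variation only. Centre size, telemonitoring use and location of initiation are site-level factors, so they cannot explain differences between patients within a site. The intervention contrast in a stepped wedge draws heavily on within-site comparisons, and that is where the unmodelled variance lies.

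This is the test that decides the trial. If its standard error is about half the true one, a strategy with no effect could be declared successful far more often than 5% of the time, and the confidence interval for the difference in days would be too short to the same degree.

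**Working it through.** **Inputs.** From section 11.1: SD 10, ICC 0.05, difference 6 days, two-sided 5%, 252 recruited, 15% drop-out, 3 patients per site in the roll-in and 1 per site per month in months 7–24. From section 4: 12 sites, two switching every three months. This gives 7 periods of 3 patients per site (12 × 21 = 252), or 2.55 per site-period after drop-out (214). Assumption: the overall mean, taken as about 12–24 days.

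**Reading the SD.** The print is garbled, but a 0–28 count cannot have an SD above 14, so 100 is impossible. As a check, a Hussey–Hughes calculation with total variance 100 and ICC 0.05 gives:

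- 3 per site-period (252): SE 1.871, power Φ(6/1.871 − 1.96) = 89.4%
- 2.55 per site-period (214): SE 2.007, power 84.8%

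An SD of 10 therefore reproduces the stated 90% at 252. The shortfall at 214 is a separate matter and is not used here.

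**Which means are possible.** For a 0–28 count the variance is at most m(28 − m). Setting m(28 − m) = 100 gives m = 14 ± √96, that is 4.2 to 23.8. An SD of 10 is possible only in that range.

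**Variance split.** Between sites 0.05 × 100 = 5; within sites 95. The Poisson model allows m within sites.

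**Size of the error.** If the reported SE is too small by a factor r, the test rejects a true null with probability 2[1 − Φ(1.96/r)]. Two versions of r:

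- Simple: r = √(100/m).
- Day scale: the Hussey–Hughes SE for 214 with within-site variance 95 (2.007 days), divided by the same SE with within-site variance m; site variance 5 in both.

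| Mean | Simple r | Rejects | Day-scale Poisson SE | Day-scale r | Rejects |
|---|---|---|---|---|---|
| 12 | 2.89 | 50% | 0.805 | 2.49 | 43% |
| 14 | 2.67 | 46% | 0.865 | 2.32 | 40% |
| 18 | 2.36 | 41% | 0.970 | 2.07 | 34% |
| 20 | 2.24 | 38% | 1.017 | 1.97 | 32% |
| 22 | 2.13 | 36% | 1.062 | 1.89 | 30% |
| 23.8 | 2.05 | 34% | 1.100 | 1.83 | 28% |

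On the day scale the correct 95% half-width is 1.96 × 2.007 = 3.9 days. The Poisson half-width would be 1.6 days at mean 12 and 2.2 at mean 23.8.

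**Simulation of the stated design.** Beta-binomial 0–28 counts with SD about 10 and ICC 0.05, no effect, 15% loss, fitted by a Poisson mixed model with a site random intercept and step effects (600–1,000 runs per setting; two sets of simulations, one of which also included three site covariates):

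| Mean | Poisson mixed model rejects |
|---|---|
| 12 | 50% |
| 14 | 43–47% |
| 16 | 42% |
| 17 | 41% |
| 18 | 37–40% |
| 20 | 35–36% |
| 21 | 34% |
| 22 | 35% |

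With Pearson-scaled standard errors the rate was 3.5–5.0% (means 14, 17 and 20). A linear mixed model gave 4.9–6.8% across the two sets. If the SD were 8 rather than 10, the Poisson model would still reject in 29% at mean 17.

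**The case against.** The strongest reply is that section 11.2.2 names a model family and an effect measure but not a variance estimator. Section 11.2 refers to a detailed SAP, which is not at hand, and robust or scaled standard errors are often fixed there. A Poisson working model with a correctly specified mean can estimate that mean under overdispersion; only its default variance fails.

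This limits the claim. A reader might infer that the trial's interval will be too narrow and its test invalid whatever the SAP says. The documents do not support that: the figures hold for model-based standard errors, and a SAP that scaled or replaced them would remove the problem. What stands is that the protocol states a specific primary model whose variance conflicts with its own planning SD. The only item section 11.2.2 expressly leaves to the SAP is missing outcome data.

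A reader might also infer that only a linear mixed model will do. That goes too far: scaling the Poisson standard errors already restores the error rate, and a linear model also ignores the ceiling at 28.

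Nor can it be shown that the power was computed for a different test. The SD and mean-difference inputs suggest a model with free variance, but the modified Stata macro cannot be inspected.

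**Conclusion.** The concern holds in conditional form. As written, the primary model allows a within-site variance of at most 28, while the sample size implies about 95, and neither the site effect nor the site-level covariates close the gap.

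With model-based standard errors and an assumed mean of about 12–24 days, the standard error is about 1.8–2.9 times too small and a nominal 5% test rejects a true null in roughly 28–50% of trials. The range covers both scales of calculation. Simulation gives about 34–47% at means of 14–21. Under the simple ratio a mean below 12 makes it worse.

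The conclusion rests on three things: reading the misprinted SD as 10, a mean the protocol does not give, and standard errors taken from the model as specified. It is not sensitive to the exact SD: at 8 days the problem remains.

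**What to change.** In section 11.2.2, require a primary model whose variance is estimated rather than fixed at the mean, with a small-sample correction for 12 clusters and the result reported as the absolute difference in mean days. Either of these would do:

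- a linear mixed model on days with the same fixed terms, a random site effect, REML and Kenward–Roger degrees of freedom, which gives the absolute difference directly and matches the inputs of section 11.1; or
- a count or beta-binomial mixed model with estimated dispersion, standardised to a difference in mean days.

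Apply the same rule to the 14-day and 28-day counts in section 8.2, and correct the printed SD in section 11.1. If the SAP already specifies such a variance, bring the protocol into line with it.

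The cost is protocol and SAP wording only. The reported interval becomes wider and correct.

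### The Poisson mixed model fixed for the primary outcome assumes a variance at least four times smaller than the SD of about 10 days used for the sample size, so its model-based 95% CI and p-value would overstate precision.

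*Protocol*

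**What the plan says.** Section 8.1 defines the primary outcome as the number of days in weeks 9-12 on which NIV is used for more than four hours. Four weeks give a range of 0 to 28 days.

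Section 11.2.2 says this count "will be analysed using a poison mixed effect model with intervention, step (time) and cluster level randomisation factors" (read: Poisson), with these "as fixed effects and site as a random effect". On reporting it says: "Effect sizes will be summarised as the absolute difference in mean days along with its 95% confidence interval and p-value". It names no dispersion parameter, robust variance, participant-level random effect or alternative count distribution. The only matter it sends explicitly to the SAP is missing outcome data; section 11.2 refers in general terms to a detailed SAP.

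Section 11.1 sizes the trial "assuming standard deviation of ten0 days with a high skew", and adds: "we assume a mean difference of six days to reflect this". It also assumes an intra-cluster correlation of 0.05, a two-sided 5% level, and 90% power with 214 evaluable participants.

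For the other scales section 11.2.2 says: "Continuous secondary outcomes will be analysed in the same way as the primary outcome".

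**The concern.** A Poisson model carries its own variance assumption: conditional on the fixed effects and the site effect, the variance equals the mean. The protocol's SD says something very different about the same variable. A site random intercept absorbs variation between sites, not variation between patients within a site, and with an intra-cluster correlation of 0.05 about 95% of the variance is of the second kind.

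If the model is fitted as named and its ordinary standard errors are used, the interval is too narrow and the p-value too small. This affects the trial's single primary test, which section 11.1 plans at a two-sided 5% level.

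**Working it through.** **Inputs.** Range 0 to 28 days (section 8.1). SD 10, intra-cluster correlation 0.05, two-sided 5%, 214 evaluable (section 11.1). Twelve sites, two switching every three months after a control roll-in (sections 4 and 7). The control mean is not stated, so the whole feasible range is used.

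**Reading the SD.** The printed figure is garbled. On a 0-28 scale the SD cannot exceed 14, so 100 is impossible. As a cross-check against the plan's own power figure, a standard stepped-wedge calculation (12 sites, 7 periods, categorical time, total SD 10, correlation 0.05, difference 6) gives 84.8% power with 214 participants and 89.4% with 252; an SD of 100 gives about 5%. The stated 90% with 214 is not reproduced exactly. That gap is a separate matter; here the check shows only that a value near 10 is meant.

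**Feasible means.** For a variable on 0 to 28 with mean m, variance ≤ m(28 − m). Setting m(28 − m) ≥ 100 gives m = 14 ± √(196 − 100) = 14 ± 9.8, so m lies between 4.2 and 23.8.

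**Dispersion.** Variance/mean = 100/m, smallest at the largest feasible mean: 100/23.8 = 4.2. Removing the 5% between-site share leaves a within-site variance of 95, and 95/23.8 = 4.0. At m = 14 the two values are 7.1 and 6.8.

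**Standard errors and error rate.** With dispersion φ, the Poisson standard error is too small by a factor √φ, and the two-sided type I error is 2[1 − Φ(1.96/√φ)].

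- Most favourable mean, 23.8: √4.2 = 2.05 on total variance, error 34%; √4.0 = 2.0 within site, error 33%, coverage 67%.
- Mean 14: √7.1 = 2.7 on total variance, error 46%; √6.8 = 2.6 within site, error 45%, coverage 55%.

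The table uses within-site variance. The last two columns come from a null simulation (500 runs per mean): beta-binomial outcomes on 0-28 with SD 10 and site correlation about 0.05, fitted by a Laplace Poisson model with a site intercept and period effects.

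| Mean | SD implied by Poisson | Within-site φ | Poisson SE / correct SE | Type I error, formula | Type I error, simulated | Simulated, SE scaled by Pearson dispersion |
|---|---|---|---|---|---|---|
| 10 | 3.2 | 9.5 | 0.32 | 52% | 57% | 5.4% |
| 14 | 3.7 | 6.8 | 0.38 | 45% | 44% | 4.4% |
| 18 | 4.2 | 5.3 | 0.44 | 39% | 36% | 3.4% |
| 22 | 4.7 | 4.3 | 0.48 | 35% | 35% | 4.6% |
| 23.8 | 4.9 | 4.0 | 0.50 | 33% | not run | not run |

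A second simulation of the same design (1,500 runs per mean) gave 46% at mean 14 and 36% at mean 20 for the Poisson mixed model, against 5.8% and 5.7% for a linear mixed model. Rescaling the same Poisson fit restores roughly the nominal level, so the variance assumption is the cause. These simulations omit the three cluster-level covariates, so they show the size of the fault but do not validate any particular replacement with 12 sites.

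**Direction.** Under the null, false rejections split about evenly: 34%/2 = 17% at mean 23.8 and 46%/2 = 23% at mean 14. A simpler simulation (sites as fixed effects, no other covariates, 600 runs) found 22% favouring the intervention at mean 14 and 18% at mean 20.

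**The case against.** The strongest reply is that the fault lies in the variance estimator, which the protocol does not fix. It names a model family and covariates, not model-based standard errors, and an SAP that is not at hand could add scaled or robust ones. With the Poisson mean model kept, the simpler simulation gave rejection rates of 4-5% with Pearson scaling, 6-6.5% with a heteroscedasticity-robust variance, and 6-7% with site-clustered errors on 11 degrees of freedom. This stands in part: the error rates above hold only for model-based standard errors, and the Poisson mean model need not be abandoned. It does not remove the defect. A Poisson model has variance equal to mean by definition, and a reader who follows section 11.2.2 as written obtains the wrong interval.

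Several stronger readings are tempting, and the protocol does not support them:

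- **That an ineffective service would be declared effective in one trial in two or three.** That counts rejections in both directions; those favouring the intervention are about 17-23% at means of 14 to 23.8.
- **That a Poisson model cannot deliver the promised difference in days.** Section 11.2.2 states neither a link nor a rate ratio, and marginal standardisation gives an absolute difference. Nor is it an error in itself to pair a normal-theory sample size with a count model.
- **That every continuous secondary interval is invalid.** No mean or SD is given for those outcomes, and the sentence may mean only the same covariates and site effect. It is ambiguous and needs clarifying.
- **That only a linear mixed model will do.** The outcome is bounded and expected to be skewed, so a normal model is also an approximation.

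**Conclusion.** The concern holds for the primary outcome. The protocol's SD and the 28-day ceiling together make the count at least 4.2 times overdispersed (about 4.0 within site), whatever the unstated control mean. Under model-based Poisson inference the standard error is at most about half its correct size, the 95% interval covers about 67% at best, and the two-sided error rate is about one third at the most favourable mean and higher below it.

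The result rests on three assumptions: the SD is about 10, weeks 9-12 mean 28 days, and standard errors are model-based with site as the only random effect. It should be corrected before analysis because it governs the primary test.

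**What to change.** Amend section 11.2.2 so that the primary analysis uses a variance valid for an overdispersed count bounded at 28 days. Any of these would serve:

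- a linear mixed model with the stated fixed effects, a site random intercept and a small-sample correction for 12 sites, which gives the difference in days directly;
- a beta-binomial mixed model with marginal standardisation to an absolute difference in days;
- the Poisson model with dispersion-scaled or robust standard errors, likewise standardised.

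Name one as primary; a second can be the sensitivity analysis. Reword the sentence on continuous secondary outcomes so that they use a linear mixed model with the same covariates and site random effect. Print the SD in section 11.1 as a clear number.

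The cost is wording and minor analysis work, with no change to recruitment or data collection. The interval will be wider than the Poisson model would report, but correct.

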# 11.3 WP3 Health Economic analysis

The initiation of NIV is estimated to cost the NHS £3,211 per year. However, the actual cost is expected to be significantly higher when factoring in the additional social care needed to support NIV use. A substantial portion of this cost comes from inpatient and emergency care, which are particularly high for MND. This includes £1,603 annually for hospital stays and £918 for emergency home visits[37]. The CE will take an NHS and personal social services cost perspective to determine the cost of non-invasive ventilation (and potential cost savings) and its cost-effectiveness.

It will be reported as incremental cost per QALY gained and net monetary benefit at 12 weeks of follow-up (within-trial analysis) and over a lifetime (decision model). Uncertainty will be shown on a CE acceptability curve and CE plane. QALYs will be derived from the EQ-5D-5L completed by the patient at w0 and w12. The mapping function developed by the NICE Decision Support Unit using the 'EEPRU dataset'[38] will be used to estimate EQ-5D-3L responses, the presently favoured iteration of EQ-5D by NICE[39]. A PPI approved service use questionnaire (low burden) will collect minimal data on the costs at baseline and subsequent follow up weeks. Hence, the analysis of resources will be of the main costs incurred in people with motor neuron disease, with the resources considered in the survey identified prior to data collection in discussions with the PPI group (likely resources to feature on the survey are high-cost episodes e.g. inpatient/emergency department visits and community appointments and those requiring travel/ambulance and a limited (no more three) high cost MND medications possibly including dosage). We collect cost data at baseline to allow for an analysis that controls for significant differences or high variability across groups.

Unit costs applied to these services will be derived from hospitals or national sources. Caregivers may be required during both day and night, as some patients may need support overnight, and where possible unit costs will reflect the excess staffing costs incurred during night care. To capture the intervention costs, we will collect the number of interactions[40], the type of professional involved in the care from trial records and if available the time of day of the interaction (day or night). We will collect the time per patient via a staff questionnaire completed by all health service staff involved on

delivering the intervention. The final administered staff survey at 12 months will collect data on the total time spent on training, preparation, troubleshooting, and other associated activities of delivering the intervention in addition to time per patient contact. This information could be collected from the dedicated staff resource survey at 12 weeks but we will explore the option of collecting this information from the NOMAD clinical team survey at week 12. In addition, we will consider using NOMAD to collect additional information on composition of the staff team, patient contacts and whether they were day/night to validate the information collected from trial records. Bootstrapped results will account for uncertainty in the trial data. The model-based lifetime extrapolation will be of resource use, survival and health utility, supplemented with longer-term survival data collected after 12 weeks. Information on the longer-term resource use and health related quality of life changes from ventilation use will be sourced from the research literature and uncertainty in these values will be explored in sensitivity testing. Where required, the analysis will adjust for baseline costs to address the expected high variability in trial costs between groups, driven by likely substantial individual differences in service use and MND-related treatments (such as emergency visits) that could potentially exceed the intervention costs by a high degree.

